Day	-28	1	8	22	43	64	84	98		
Day Visit Window	+7/ -14		±1	±2	±2	±2	±2	±3		
Spot urine from first morning void over 3 consecutive days: albumin, creatinine (central laboratory)		X		X	X		X	X	Spot urine from first morning void over 3 consecutive days, ideally on day of clinic visit and preceding 2 days, collected at home in provided vials. Analysis will be done in all 3 samples at central laboratory and averaged.	Section 8.1.1
Spot urine from first morning void: Na ⁺ , K ⁺ , uric acid, urea, glucose, creatinine, osmolality, and cortisol (central laboratory)		X		X	X		X	X	Spot urine from first morning void, only from the third day sample (day of clinic visit), collected at home in provided vial. Analysis will be done at central laboratory.	Sections 8.5.3 and 8.5.3.1
Body weight	X	X	X	X	X		X	X	Body weight must be taken and reviewed before treatment at each dosing visit.	Sections 8.2.2 and 5.1
Echocardiography	X						X		Screening and Week 12 only. ECHO will be performed locally and sent to central reader. Results need to be available before randomisation.	Section 8.1.3.3
Bioimpedance spectroscopy		X	X	X	X		X	X		Section 8.1.3.2
Home-based monitoring										
Daily digital body weight measurement		Daily home measurement using a digital device from randomisation to end of follow up.							Home body weight measurements should start 2 days before randomisation (same as for spot urine).	Section 8.1.3 and Section 8.2.1

Procedure	Screening	Interventional period							Follow-up	Notes	Details in CSP Section/Appendix
		1	2	3	4	5	6	7 (ED)			
Visit	1	2	3	4	5	6	7 (ED)	8			
Week	-4	0	1	3	6	9	12	14			
Day	-28	1	8	22	43	64	84	98			
Day Visit Window	+7/ -14		±1	±2	±2	±2	±2	±3			
Pharmacodynamics											
Plasma/serum K ⁺ , Na ⁺ , uric acid, BUN, fasting plasma glucose, cystatin C, haematocrit, haemoglobin, ET-1, ELDP, CT-proET-1, copeptin, NT-proBNP, and BNP (central laboratory)	X	X	X	X	X	X	X	X	Results for central BNP testing must be reviewed within 24 hours of receipt by the investigator.	Section 8.2.4 and 8.5.3.1	
BNP or NT-proBNP (local laboratory)	X								Results need to be available before randomisation.	Section 8.2.4	
Safety assessments											
Adverse event review	X SAEs only	X	X	X	X	X	X	X		Section 8.3	
Vital signs (blood pressure, pulse, respiratory rate)	X	X	X	X	X	X	X	X	Vital signs at Visit 2 need to be performed and the results reviewed before randomisation in IWRS.	Section 8.2.2 and 8.1.2.1	

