Digital 12-lead safety ECG	X	X	X	X	X	X	X	X	ECGs will be centrally read. ECG read out from Visit 2 to be reviewed by the investigator before randomisation as central report will not be available on the day. Unscheduled ECGs may be added if clinically indicated.	Section 8.2.3	

Procedure	Screening	Interventional period						Follow-up	Notes	Details in CSP Section/Appendix
		2	3	4	5	6	7 (ED)			
Visit	1	2	3	4	5	6	7 (ED)	8		
Week	-4	0	1	3	6	9	12	14		
Day	-28	1	8	22	43	64	84	98		
Day Visit Window	+7/ -14		±1	±2	±2	±2	±2	±3		
Clinical chemistry and haematology (central laboratory)	X	X	X	X	X	X	X	X	Central laboratory results must be reviewed by investigator within 48 hours from receipt of result, and eGFR and creatinine calculations made, and participant discontinued if required. Clinical chemistry includes creatinine and eGFR calculation using the CKD-EPI formula in both ways: based on cystatin C and based on creatinine.	Sections 8.1.2.2 and 8.2.4
Urinalysis (central laboratory)	X	X		X			X	X		Section 8.2.4
HbA1c, cholesterol and lipids (central laboratory)	X	X					X	X		Section 8.2.4
Study intervention										
Study intervention dispensed		X		X	X	X				Section 6.2, 6.3, 6.4
Study intervention account				X	X	X	X			Section 6.2, 6.4
Study intervention intake at the clinic		X		X		X			Between the clinic visits and at Visits 3, 5 and 7, participants will take their study intervention at home. At Visits 4 and 6, study intervention will be taken in the clinic irrespective of participation in the PK sub-study.	Section 6.2, 6.3, 6.4

Procedure	Screening	Interventional period						Follow-up	Notes	Details in CSP Section/Appendix
		1	2	3	4	5	6			
Visit	1	2	3	4	5	6	7 (ED)	8		
Week	-4	0	1	3	6	9	12	14		
Day	-28	1	8	22	43	64	84	98		
Day Visit Window	+7/ -14		±1	±2	±2	±2	±2	±3		
Pharmacokinetics										
4-hour PK blood sample profile				X					Total of 5 samples, spread over 5 time points: Pre-dose, 0.5-1.0 h, 1.5-2.0 h, 2.5-3.0 h, 3.5-4.5 h post-dose. Performed in the morning. Dose taken at clinic. Participants to arrive fasted at clinic (light breakfast provided). Participants to stay at clinic until last PK post-dose sample has been taken. Zibotentan and dapagliflozin plasma concentrations will be measured separately. If participants or investigators do not wish to participate in this sub-study, only one pre-dose sample (separate tubes for zibotentan and dapagliflozin) will be taken instead of the whole profile.	Section 8.5.1.1

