4.2 General Presentation Considerations

4.2.1 Study Period

The following study periods are defined (if the specified visit did not take place, the date for planned visit should be used):

- Overall study period – from date of Visit 1 to date of Visit 8
- Screening period – from date of Visit 1 up to the day before Visit 2; this can be up to approximately 4 weeks in duration prior to randomisation
- Treatment (Interventional) period – from date of Visit 2 to date of Visit 7
- On-treatment period – from the same date as the first administration of study intervention until the earliest of: 28 days after last dose of zibotentan/placebo and/or dapagliflozin/placebo; end of study; lost to follow-up; and withdrawal of consent
- Off-treatment period – from more than 28 days after the last dose of study intervention
- Follow-up period – from day after Visit 7 to date of Visit 8

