For continuous variables, descriptive statistics will include the number of non-missing observations (n), mean, standard deviation (SD), median, minimum and maximum. For log-normal variables, the geometric mean (GeoMean) and coefficient of variation (CV) will be presented in addition to those already specified for continuous variables. Continuous data that are expected to be skewed (e.g. duration of exposure, time on study and laboratory variables) will be presented in terms of the maximum, upper quartile, median, lower quartile, minimum and number of observations. The minimum and maximum will be reported to the same number of decimal places as the raw data recorded in the database. The mean, median, lower quartile and upper quartile will be reported to one more decimal place than the raw data recorded in the database. The SD will be reported to two more

decimal places than the raw data recorded in the database. In general, the maximum number of decimal places reported shall be four for any summary statistic.

Categorical variables will be summarised using frequency counts and percentages. Percentages will be presented to one decimal place. Percentages will not be presented for zero counts. Percentages will be calculated using the number of non-missing observations as the denominator, unless otherwise specified in the TLF mock shells. If sample sizes are small, the data displays will show the percentages, but any textual report will describe frequencies only.

P-values greater than or equal to 0.001, in general, will be presented to three decimal places. P-values less than 0.001 will be presented as “<0.001”.

Confidence intervals will be presented to one more decimal place than the raw data.

Data will be summarised by visit, as appropriate. For information on analysis visit windows, please refer to Section 4.2.3

‘Baseline’ is defined as the last non-missing value obtained prior to or on the same date as the administration of the first dose of study treatment, unless otherwise stated. For participants without a first dose, the last non-missing value obtained prior to or on the same date as the randomisation date will be used for ‘baseline’. ‘End of Study’ is defined as the last available post-treatment assessment. ‘Study Day’ will be calculated relative to the date of first dose of study treatment i.e.:

if Assessment Date < Date of First Dose of Study Treatment, then

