4.11.5 Vital Signs, Electrocardiograms, Echocardiography and Other Observations Related to Safety

The number and percentage of participants with normal and abnormal ECG readings by visit will be presented by treatment arm. Abnormal ECG results and reasons entered into the eCRF will be listed by participant and by visit.

For by-visit summaries, the last non-missing assessment (including repeat assessments) recorded at each applicable scheduled visit will be summarised.

The following summaries will be provided:

- A summary, which will cover n, mean, SD, minimum, Q1, median, Q3, and maximum, of the observed absolute values and change from baseline for all vital sign parameters by treatment arm and time point.
- A summary of key participant information for participants reporting notable changes outside predefined criteria for all vital sign parameters.

- A summary of the number and percentage of participants experiencing notable changes from baseline outside predefined criteria, by vital sign parameter and treatment arm.
- A summary of the observed absolute values and change from baseline in each ECG parameter (excluding QTcB) by treatment arm and time point.
- A summary of ECG assessment (normal/abnormal [clinically significant, not clinically significant]), baseline versus last observation on treatment.
- A summary of key participant information for participants reporting PCS ECG values (excluding QTcB) outside predefined criteria.
- A summary of the number and percentage of participants reporting PCS ECG values (excluding QTcB) outside predefined criteria, by ECG parameter and treatment arm.
- A summary of the overall evaluation for echocardiography (normal/abnormal) and LVEF by treatment arm and time point.

By-participant listings of vital sign parameters, ECG parameters, ECG findings, echocardiography parameters, and weight, height and BMI will also be provided.

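### For completers seen in window at Visit 8, the 28-day rule makes the Week 14 ECG, taken after dosing has ended, the last on-treatment value in the ECG shift table

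*SAP*

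**What the plan says.** **Periods.** SAP 4.2.1 starts the on-treatment period on the date of first dose and closes it at the earliest of "28 days after last dose of zibotentan/placebo and/or dapagliflozin/placebo; end of study; lost to follow-up; and withdrawal of consent". The same section defines the follow-up period as "from day after Visit 7 to date of Visit 8". SAP 4.2.2 says that a participant's end of study "is defined as the last available post-treatment assessment".

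**Schedule.** SAP Table 5 (4.2.3) gives protocol windows of Day 82 to 86 for Visit 7 and Day 95 to 101 for Visit 8. It maps assessments on Day 92 to 129 to an analysis visit called Follow-up. The protocol's Schedule of Activities (1.3) has the last doses taken at home: "Between the clinic visits and at Visits 3, 5 and 7, participants will take their study intervention at home". Its row "Digital 12-lead safety ECG" is marked at every visit, including Visit 8.

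**Outputs.** SAP 4.11 bases safety summaries on the 4.2.1 on-treatment period unless something else is specified. SAP 4.11.5 specifies nothing else for the ECG normal/abnormal table, which is "baseline versus last observation on treatment". The same section also says: "The number and percentage of participants with normal and abnormal ECG readings by visit will be presented by treatment arm".

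**Fluid events.** SAP 4.11.5.1 gives an on-treatment rate per 100 participant exposure years. For a participant without an event, time at risk ends by the same 28-day rule. SAP 4.11.1 counts duration of exposure from first to last dose only.

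**The concern.** A 28-day window is longer than the follow-up this trial has. Visit 8 is planned about two weeks after the last dose, so for most completers the window never closes before the study does. Where a table takes the last value in the window, the follow-up value then displaces the value obtained while the participant was still dosing.

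That is the case for the ECG shift table. A reader who sees an on-treatment heading will take it as ECG status at the end of dosing. For in-window completers with a Week 14 ECG it is instead their status some two weeks after both drugs were stopped. The by-visit tables will present the same tracing as follow-up.

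The fluid-event rate raises a smaller matter. Fluid retention is the designated event of special interest, and a rate per exposure year will be read as a rate over time on drug. Its denominator includes the undosed follow-up weeks.

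**Working it through.** **Inputs.** First dose is on Day 1. Visit 7 is on Day 84 (82 to 86) and Visit 8 on Day 98 (95 to 101), from SAP Table 5 and protocol 1.3. A completer's last dose is taken on the day of Visit 7, from the protocol's home-dosing note. End of study for the participant is the Visit 8 date, from SAP 4.2.2.

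**Step 1: reproduce the plan's own figures.** 84 ± 2 gives Day 82 to 86, and 98 ± 3 gives Day 95 to 101, as in Table 5. The nominal gap is 98 − 84 = 14 days, which agrees with the stated interval of about two weeks.

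**Step 2: where the on-treatment period ends.**

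| Last dose (Visit 7) | Last dose + 28 | Latest in-window Visit 8 |
|---|---|---|
| Day 82 | Day 110 | Day 101 |
| Day 84 | Day 112 | Day 101 |
| Day 86 | Day 114 | Day 101 |

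Visit 8 always comes first. The gap from last dose to Visit 8 runs from 95 − 86 = 9 to 101 − 82 = 19 days. If the last dose was taken the day before Visit 7, the longest gap is 20 days, still below 28. The whole follow-up period therefore lies inside the on-treatment period.

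If end of study were read as the trial-level date in protocol 4.4, the window would run to last dose + 28. It would still contain Visit 8, so the ECG result does not depend on that choice.

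**Step 3: limit of the result.** With the last dose on Day 84, the window closes on Day 112. A Visit 8 on Day 113 to 129, which Table 5 still accepts as follow-up, would be off treatment. The point is therefore confined to visits in window.

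**Step 4: the ECG table.** An ECG is scheduled at Visit 8, Visit 8 is inside the window, and the table takes the last value in the window. The Week 14 ECG is selected whenever it is present.

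**Step 5: the fluid-event denominator, for an event-free completer.** Time at risk = min(last dose + 28, end of study) − first dose + 1. Exposure under 4.11.1 = last dose − first dose + 1.

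| Visit 7 / Visit 8 | Time at risk | Exposure | Ratio |
|---|---|---|---|
| Day 84 / Day 98 | 98 | 84 | 98/84 = 1.167 |
| Day 86 / Day 95 | 95 | 86 | 95/86 = 1.105 |
| Day 82 / Day 101 | 101 | 82 | 101/82 = 1.232 |

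**Step 6: does this bias the rate?** BNP, site weight and bioimpedance are scheduled at Visit 8, so events found there enter the numerator as well. Suppose the event hazard in the two weeks after dosing is k times the hazard on drug. The documents give no value for k; I assume a range of 0 to 3. For a nominal completer the rate changes by the factor (84 + 14k)/98:

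- k = 0: 0.857
- k = 1: 1.000
- k = 3: 1.286

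The direction depends entirely on an unknown.

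**The case against.** **A 28-day lag is ordinary practice.** Adverse events are collected through Visit 8, nothing says that on-treatment and follow-up must be exclusive, and a lag for attributing events is a normal choice. This stands for adverse events, and I would not change it there. It does not carry over to a last-observation table, where the later value replaces the on-drug one.

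**The ECG information is reported elsewhere.** Counts by visit, values and changes by time point, tables of potentially significant values and listings are all planned. This stands and limits the loss to one cross-tabulation. SAP 4.11 also allows exceptions, and the mock shells, which might contain one, are not available to us.

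**Stronger readings that the documents do not support.**

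- *The fluid-event rate is biased or diluted.* SAP 4.11.5.1 writes out its own formula, and numerator and denominator cover the same window. Step 6 shows that no direction follows, and no effect on a whole arm's rate has been shown. The relative risk against dapagliflozin, with its Katz-log standard error, does not use this time denominator.
- *Section 4.11.1 sets a competing end of treatment because its Kaplan-Meier figure stops completers at Visit 7 or Day 86.* That is a censoring rule for premature discontinuation, which cannot occur once planned dosing is over. It says nothing about time at risk for fluid events.
- *On-drug fluid data are missing from the plan.* Body weight is summarised over the interventional period, fluid volumes and BNP over time, and a by-participant listing is planned.
- *Every on-treatment output is compromised.* In the laboratory maximum and minimum shifts, the Hy's Law maxima, the treatment-emergent flags and the adverse event tables, the Visit 8 data are added to the on-drug data and do not replace them.

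**Conclusion.** The point holds for the ECG shift table and is minor. As SAP 4.2.1, 4.11 and 4.11.5 are written, each completer with an in-window Visit 8 and a Week 14 ECG enters that table with a tracing taken 9 to 19 days (nominally 14) after the last dose. What is lost is the comparison of baseline with the end of dosing.

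The fluid-event rate is internally consistent. Only its name misleads: 98 days are counted as exposure for a nominal event-free completer who had 84 under 4.11.1, which is 16.7% more.

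The conclusion assumes that the last dose is taken on the day of Visit 7 and that no unseen shell overrides 4.11.5. Off drug here means after the last dose: the documents give no half-life, so residual drug in the first days cannot be judged. The primary endpoint is not touched.

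**What to change.** 1. **ECG shift table.** Define the last on-treatment ECG as the last non-missing post-baseline ECG on or before the date of last dose, normally Visit 7 for completers. Use this single date. A rule that also allowed the visit at which dosing ends would give two dates for someone who stops between visits. Show Week 14 separately as follow-up, and footnote that the other ECG outputs keep the 28-day window.
2. **Fluid-event rate.** Keep the calculation and rename it as a rate per 100 participant-years to 28 days after last dose or end of study.
3. **Optional.** Add one rate restricted to the time from first to last dose, stopped at the first event, with a numerator to match.

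**Cost.** One changed flag, one footnote and one label; the optional row is one more line. Section 4.11.5 would carry two ECG windows, which is why the footnote is needed. A completer whose last dose was the day before Visit 7 would be represented by an earlier ECG, so the number affected should be stated. The optional row would have fewer events and would omit those first detected after dosing stops; these remain in the existing rates.

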4.2.2 Data Presentation

All efficacy and safety variables will be summarised by study treatment arm using descriptive statistics. The type of analysis that will be performed for a treatment arm – main (M) or only descriptive (D) – depends on the protocol version and study part as specified in Table 4. Note that descriptive analysis will also be performed for M as a way of presenting data as detailed in this SAP.

For treatment arms marked with D in Table 4, a selection of descriptive statistics will be presented. The outputs will be identified in the tables, listings and figures (TLF) mock shells. The following information will be part of these selected outputs:

- Disposition
- Demographics
- Baseline characteristics
- UACR descriptive summary
- AEs/SAEs/DAEs
- Vital signs
- Clinical laboratory tests (including eGFR)
- 12-lead ECG assessment
- Event of special interest (changes in fluid-related measures)
- Study site body weight and total body water
- Exposure
- PK.

Table 4 Protocol version, study part, treatment arm and type of analysis

Study part Treatment arm	Protocol Version 1.0 and CSP Amendment 1		CSP Amendment 2
	A	B	-
Placebo once daily	X/D	X/D	
Zibotentan 5 mg once daily	X/D	X/D	
Dapagliflozin 10 mg once daily	X/D	X/M	X/M
Zibotentan 5 mg + Dapagliflozin 10 mg once daily	X/D	X/D	
Zibotentan 1.5 mg + Dapagliflozin 10 mg once daily		X/M	X/M
Zibotentan 0.25 mg + Dapagliflozin 10 mg once daily		X/M	X/M

X marks whether the treatment arm is included under the corresponding protocol version and study part, M marks the treatment arms that are included in the main analysis and D marks the treatment arms that will only be presented with descriptive statistics.

For continuous variables, descriptive statistics will include the number of non-missing observations (n), mean, standard deviation (SD), median, minimum and maximum. For log-normal variables, the geometric mean (GeoMean) and coefficient of variation (CV) will be presented in addition to those already specified for continuous variables. Continuous data that are expected to be skewed (e.g. duration of exposure, time on study and laboratory variables) will be presented in terms of the maximum, upper quartile, median, lower quartile, minimum and number of observations. The minimum and maximum will be reported to the same number of decimal places as the raw data recorded in the database. The mean, median, lower quartile and upper quartile will be reported to one more decimal place than the raw data recorded in the database. The SD will be reported to two more

decimal places than the raw data recorded in the database. In general, the maximum number of decimal places reported shall be four for any summary statistic.

Categorical variables will be summarised using frequency counts and percentages. Percentages will be presented to one decimal place. Percentages will not be presented for zero counts. Percentages will be calculated using the number of non-missing observations as the denominator, unless otherwise specified in the TLF mock shells. If sample sizes are small, the data displays will show the percentages, but any textual report will describe frequencies only.

P-values greater than or equal to 0.001, in general, will be presented to three decimal places. P-values less than 0.001 will be presented as “<0.001”.

Confidence intervals will be presented to one more decimal place than the raw data.

Data will be summarised by visit, as appropriate. For information on analysis visit windows, please refer to Section 4.2.3

‘Baseline’ is defined as the last non-missing value obtained prior to or on the same date as the administration of the first dose of study treatment, unless otherwise stated. For participants without a first dose, the last non-missing value obtained prior to or on the same date as the randomisation date will be used for ‘baseline’. ‘End of Study’ is defined as the last available post-treatment assessment. ‘Study Day’ will be calculated relative to the date of first dose of study treatment i.e.:

if Assessment Date < Date of First Dose of Study Treatment, then

$$\text{Study Day} = \text{Assessment Date} - \text{Date of First Dose of Study Treatment}$$

else if Assessment Date ≥ Date of First Dose of Study Treatment, then

$$\text{Study Day} = \text{Assessment Date} - \text{Date of First Dose of Study Treatment} + 1$$

If the date of first dose of study treatment is not present, the randomisation date will be used in the above calculations.

4.2.3 Analysis Visit Windows

All visit-based summaries will use analysis visits. All post-randomisation scheduled and unscheduled visits (excluding Discontinuation visit), will be mapped to an appropriate analysis visit as shown in Table 5.

Table 5 Analysis Visit Windows

CRF Visit	Target Day ¹	Protocol Visit Window ¹	Actual Assessment Day ²	Analysis Visit
Visit 3 (Wk 1)	D8	D7 to D9	D2 to D15	Week 1
Visit 4 (Wk 3)	D22	D20 to D24	D16 to D32	Week 3
Visit 5 (Wk 6)	D43	D41 to D45	D33 to D53	Week 6
Visit 6 (Wk 9)	D64	D62 to D66	D54 to D74	Week 9
Visit 7 (Wk 12)	D84	D82 to D86	D75 to D91	Week 12
Visit 8 (Wk 14)	D98	D95 to D101	D92 to D129	Follow-up

¹Relative to the date of randomisation

²Relative to the date of first dose of study treatment or randomisation date if no first dose

For visit-based summaries, if there is more than one value per participant within a time window, then the closest value will be summarised, or the earliest in the event the values are equidistant from the

nominal visit date. The listings will highlight the value for that participant that went into the summary table, wherever feasible.

